### **1.2 Purpose**

This extension study (CAIN457A2302E1) is planned to collect an additional four years of long-term efficacy, safety, and tolerability data of secukinumab in either continuous or interrupted therapy (randomized withdrawal period) in subjects completing either one of the two phase III studies CAIN457A2302 or CAIN457A2303 (and potentially other secukinumab phase III studies) and showing at least partial response to secukinumab at Week 52 of the core study. An interim analysis on safety data only and a primary endpoint analysis (PEA) up to Week 68 will be conducted.

The data collected in this study up to the time of the interim analysis will be part of the submission package. The data collected beyond the time of the Week 68 interim analysis will deliver important information on the effect of long-term treatment of chronic plaque-type psoriasis with secukinumab. Additional interim analyses may be conducted at various time points for publications or health authority requests.

The two year double-blind randomized withdrawal period will allow assessing whether continuation of treatment with secukinumab is of benefit to subjects after having been treated with secukinumab for up to 52 weeks in the preceding phase III studies, compared to stopping treatment with secukinumab. In addition, this treatment period will deliver important information on the effect of stopping treatment with secukinumab, including time to relapse (i.e., loss of  $\geq 50\%$  of previous gain in PASI reduction) and frequency of rebounds, and therefore addresses needs brought forward by Health Authorities. The two year double-blind period of the study will be followed by a two year open label period. During the open label treatment period, subjects initially on the lower dose (150 mg) will be offered to switch to the higher dose (300 mg), at the discretion of the investigator. This allows all subjects in the study to receive the most efficacious dose of secukinumab.

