### 2.2 Secondary objectives

- To assess the efficacy of secukinumab 150 mg or 300 mg with respect to PASI 50/75/90/100 response and IGA 0 or 1 response, compared to placebo over time in subjects who were PASI 75 responders at Week 52, over time for subjects who were re-treated after relapse with secukinumab 150 mg or 300 mg, and over time in subjects who were partial responders at Week 52
- To assess the efficacy of secukinumab 150 mg or 300 mg with respect to PASI score and IGA mod 2011 score, compared to placebo over time in subjects who were PASI 75 responders at Week 52, over time for subjects who were re-treated after relapse with secukinumab 150 mg or 300 mg, and over time in subjects who were partial responders at Week 52
- To assess time to PASI 75 response **for subjects who were re-treated after relapse with secukinumab 150 mg or 300 mg.**
- To assess the efficacy of secukinumab 150 mg or 300 mg in subjects with moderate to severe chronic plaque-type psoriasis with respect to loss of IGA 0 or 1 response, compared

to placebo **in subjects who were PASI 75 responders and IGA 0 or 1 responders at Week 52.**

- To assess time to IGA 0 or 1 response for subjects who were IGA 0 or 1 responders at re-randomization, and who lost IGA 0 or 1 response during randomized withdrawal, and **who were re-treated after relapse with secukinumab 150 mg or 300 mg.**
- To assess the clinical safety of secukinumab 150 mg or 300 mg as assessed by vital signs, clinical laboratory values, electrocardiograms (ECGs), and adverse events (AEs) monitoring, compared to placebo in subjects who were PASI 75 responders at Week 52, in subjects who were re-treated after relapse with secukinumab 150 mg or 300 mg, and in subjects who were partial responders at Week 52.
- To assess the efficacy of secukinumab 150 mg or 300 mg in subjects with moderate to severe chronic plaque-type psoriasis with respect to changes in Dermatology Life Quality Index® (DLQI®), compared to placebo over time in subjects who were PASI 75 responders at Week 52, over time for subjects who were re-treated after relapse with secukinumab 150 mg or 300 mg, and over time in subjects who were partial responders at Week 52.

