### **3.3 Rationale of dose/regimen, duration of treatment**

The doses and regimens selected for secukinumab are projected to deliver high efficacy while at the same time ensuring subject safety. The proposal to continue treatment with s.c. doses of 150 mg and 300 mg administered every four weeks, as well as the additional treatment duration of 208 weeks (leading to an overall treatment period [core plus extension] of 260 weeks) is based on the need for efficacy and safety information during chronic treatment in subjects suffering from chronic plaque-type psoriasis.

The rationale of the dose/regimen for re-treatment after full relapse is supported by model-based considerations. These model-based predictions are subject to caveats and assumptions, but appear to provide plausible guidance. The predictions are considered as extrapolations, as they are made for regimens, time points, subject subsets and withdrawal/re-treatment patterns for which limited or no data is available, as they have not (or not in exactly this way) been studied so far (which is the nature of the current status of development of secukinumab in psoriasis).

The inclusion of a randomized withdrawal treatment period will allow assessing time to relapse and frequency of rebound after cessation of treatment, compared to continuous treatment. This is in line with guidelines for the development of drugs to treat psoriasis ([CHMP/EWP/2454/02](#)).

[figure not shown]
The switch from the lyophilisate to the more convenient prefilled syringe is supported by the results of clinical study CAIN457A2106, which has shown that the exposure profiles of both formulations are virtually identical. This will also remove the need to have unblinded pharmacists involved in the study; these were necessary in the core studies to ensure the double-blind.

Model-based predictions in [Figure 3-2](#) suggest:

- Subjects lose PASI 75 response after withdrawal at an approximate rate of 10% per month (see [Figure 3-2](#) left).

- Substantially less subjects show a full relapse, the predictions reaching 10% after four months (see [Figure 3-2](#) right).

[figure not shown]
**Figure 3-2 Model-based prediction of % PASI 75 responders and % of subjects relapsing during a period of 6 months after either continuous treatment or of withdrawal (based on responders at Week 52)**

Model base exploration with high and unquantifiable uncertainty, thus no intervals are provided

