## **9.5.2 Safety variables**

All safety evaluations will be performed on the Safety set. For adverse events an analysis based on pooled treatment groups “any secukinumab 150 mg” and “any secukinumab 300 mg” will also be done. In the analysis of the subjects who were re-treated after relapse with secukinumab 150 mg or 300 mg only safety data after re-treatment after relapse will be reported. With the exception of adverse events that qualify as "treatment emergent" (see definition below), data collected from telephone visits and unscheduled visits in follow-up period 2 will only be included in individual patient listings, but not in summary tables.

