## 1.1 Statistical and analytical plans

The planned analysis is described in Section 9 (Data Analysis) of the study protocol which is available in Appendix 16.1.1 of the CSR.

This document mainly covers statistical and analytical plans for the final analysis after database lock. The key analyses which conducted previously might be re-run using the final data.

The key secondary analyses during RW period using the final data will be re-run for PASI 75 responders at week 52. The re-run analyses are including summary and analysis of PASI 50/75/90/100 response and IGA 0 or 1 response, loss of PASI 75/IGA 0 or 1 response, time to relapse, and DLQI. Since loss of PASI 75 during randomized withdrawal period will be re-run, the primary endpoint – loss of PASI 75 up to week 68 will not be performed in the final analysis. In addition, a summary of PASI 50/75/90/100 response and IGA 0 or 1 response and IGA 0 or 1 response till week 156 will also be provided using retreatment patients after relapse.

Summary statistics for continuous variables will include N, mean, standard deviation, minimum, lower quartile, median, upper quartile, maximum. Summary statistics for discrete variables will be presented in contingency tables and will include absolute and relative frequencies.

If not otherwise specified, p-values will be presented as two-sided p-values and two-sided confidence intervals will be displayed.

Unless otherwise stated, the level of significance will be set to 5% (two-sided, family-wise type-I-error).

All listings will be presented by treatment sequence.

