#### Table 1-3 Treatment groups by subjects group for safety analysis

 Any AIN457 150 mg group includes all the subjects who have ever received at least one dose of AIN457 150 mg from Week 52 to Week 256 (Week 260 EOT no dose), regardless whether they are initial PASI 75 responder or partial responder at Week 52. For the subjects assigned to placebo group at Week 52 and switched to AIN457 150 mg after relapse or started AIN457 150 mg during open label period, the safety data during and after 1st AIN457 dose will be included in this group. For subjects starting with 150 mg AIN457 dose and switched to 300 mg AIN457, the period used the low dose will be counted for the 'Any AIN457 150mg' group.

 Any AIN457 300 mg group includes all the subjects who have ever received at least one dose of AIN457 300 mg from Week 52 to Week256 (Week 260 EOT no dose), regardless whether they are initial PASI 75 responder or partial responder at Week 52. For the subjects assigned to placebo group at Week 52 and switched to AIN457 300 mg after relapse or started AIN457 300 mg during open label period, the safety data during and after 1st AIN457 dose will be included in this group. For subjects starting with 150 mg AIN457 dose and switched to 300 mg AIN457 at any time, the period after switching to the high dose will be included in the 'Any AIN457 300 mg' group.

 AIN457 150mg – Placebo group includes the PASI 75 responders who were assigned AIN 457 150mg during core study, and randomized to placebo at week 52. Only data for subjects received placebo period were included in safety analysis.

 AIN457 300mg – Placebo group includes the PASI 75 responders who were assigned AIN 457 300mg during core study, and randomized to placebo at week 52. Only data for subjects received placebo period were included in safety analysis.

So, for re-run efficacy analysis the data will be analyzed for RW period. Regarding retreatment patients after relapse, the data till week 156 will be presented. For data analysis till week 156, the following treatment groups will be reported

#### • Subjects who were PASI 75 responders at Week 52

AIN457 150 mg AIN457 300 mg AIN457 150mg - Placebo AIN457300mg - Placebo

• Subjects who were re-treated after relapse with secukinumab 150 mg or 300 mg

AIN457 150 mg AIN457 300 mg Placebo - AIN457 150 mg Placebo - AIN457 300 mg

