For final analysis, the following treatment groups will be reported for the on treatment period.

AIN457 150 mg stay AIN457 300 mg stay All AIN457 150 mg All AIN457 300 mg AIN457 150 mg only AIN457 150 mg - 300 mg AIN457 300 mg only

The following study periods will be considered for analysis:

- Screening period (before Randomization in extension)
- **Randomized** withdrawal (RW) period for subjects who were PASI 75 responders at Week 52- the duration of RW period for each subject is different i.e., starting from Week 52 until the subject experiences the first full relapse for efficacy analyses and until the subjects reinitiating the secukinumab after first full relapse for safety analyses. RW period is not fixed for all the subjects but varies for subject to subject based on occurrence of relapse. Subjects not experiencing the relapse will end their RW period at Week 156.
- **Treatment** period for subjects with relapse (for efficacy analyses it is starting from the visit in RW period at which a subject experiences first full relapse to Week 156. Safety analysis will not be re-run for subjects with relapse).
- **Treatment** period for subjects with partial response (Week 52 to Week 156)
- **Open label** period for subjects who were continued in the study and were unblinded at Week 156. The first open label dose were given at the site at Week 156. Subjects previously randomized to receive 150 mg secukinumab may continue with 150 mg secukinumab open label or may switch to 300 mg s.c. at the discretion of the investigator. Subjects previously randomized to 300 mg secukinumab continued with 300 mg secukinumab open label. Placebo subjects who entered the open label period were given once weekly s.c. injections of secukinumab for 4 consecutive weeks and then s.c. injections every 4 weeks. Any subject starting on secukinumab 150 mg may continue on 150 mg every 4 weeks or switch to 300 mg at Week 156 or any other regular site visit if the investigator decided the subject would benefit from the higher dose. The Week 244 visit was the last scheduled visit at which the subjects were allowed to switch to 300 mg dose. Decreasing the dose from 300 mg to 150 mg was not allowed.
- Follow-up (FU) period (for all subjects)\*: treatment free period (Week 264 to Week 268).

Novartis	Confidential	Page 15
RAP Module 3	9-Apr-2018 (1:15)	Secukinumab / AIN457A2302E1

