# 1.10 Standard safety evaluation

All safety analyses will be based on the safety set. In general, summaries will be provided for extension phase i.e after first dose of study medication in extension. In general, extension baseline will be used for all change from baseline analysis.

Safety analysis will be based on treatment groups as defined in Table 1-3.

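### The SAP's final analysis gives no separate safety summary for subjects re-treated after relapse, although the protocol makes this a secondary objective with its own analysis group

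*Protocol*

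**What the plan says.** **Protocol.** The clinical safety objective in 2.2 covers vital signs, laboratory values, ECGs and adverse events. Besides the comparison with placebo, it asks for safety "in subjects who were re-treated after relapse with secukinumab 150 mg or 300 mg, and in subjects who were partial responders at Week 52". Section 9 lists re-treated subjects as an analysis group at each dose. Section 9.5.2 specifies that for this group "only safety data after re-treatment after relapse will be reported". Section 1.2 gives the study's purpose as long-term data on "secukinumab in either continuous or interrupted therapy (randomized withdrawal period").

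**SAP.** Section 1.1 sets the scope: "This document mainly covers statistical and analytical plans for the final analysis after database lock". In the study periods listed in SAP 1.3, the entry on relapsed subjects states: "Safety analysis will not be re-run for subjects with relapse". Section 1.10 adds: "Safety analysis will be based on treatment groups as defined in Table 1-3". For the entire study period that table has three Any AIN457 columns (150 mg, 300 mg, any dose) and two columns for time on placebo. No column is for re-treated subjects. Footnote 1 puts into Any AIN457 150 mg the placebo subjects who "switched to AIN457 150 mg after relapse or started AIN457 150 mg during open label period", from their first active dose. Footnote 2 does the same for 300 mg.

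SAP 1.4 plans no subgroup analyses. SAP 1.1.1, the list of changes from the protocol's methods, does not mention re-treated safety.

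**The concern.** Table 1-3 shows safety during the drug-free period but has no column for safety once the drug is restarted. Placebo relapsers, who restart with weekly loading doses, are counted with never-withdrawn responders, partial responders and open-label starters. An excess of events confined to re-exposed subjects would be averaged with the rest of the column.

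For efficacy the separation already exists: Table 1-2 defines Placebo - AIN457 150 mg and Placebo - AIN457 300 mg. The safety set in SAP 1.2 also still includes re-treated subjects. The final safety tables therefore omit a named objective that existing data and derivations could answer.

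**Working it through.** **1. The conflict needs no arithmetic.** Protocol 2.2, 9 and 9.5.2 require a re-treated safety summary. SAP 1.3 does not repeat it, Table 1-3 has no column for it, and SAP 1.4 closes the subgroup route. SAP 1.1.1 is silent.

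**2. Inputs for size.** The documents give no figure for the number re-treated or for dilution, so there is none to reproduce.
- Arm sizes (Protocol 9.7, SAP 1.11): 414 per dose at 2:1 gives 414 x 2/3 = 276 active and 414/3 = 138 placebo, as stated. Over both doses, placebo is 2 x 138 = 276.
- Total subjects: about 1,220 planned (Protocol 4) or 1,146 randomized (Protocol, Amendment 2). Assuming an equal split by dose, N = 610 or 573 per dose.
- Assumptions: a fraction r = 25% to 100% of placebo subjects relapse and are re-treated, and either all or none of the non-relapsers start open label.

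**3. Dilution.** The re-treated share of one dose column is w = 138r/N if all non-relapsers start open label, and w = 138r/(N - 138 + 138r) if none do. If re-treated subjects have RR times the risk of everyone else in the column, the pooled column shows 1 + w(RR - 1).

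| r | Re-treated per dose | Lowest w | Highest w | Shown if RR = 2 | Shown if RR = 3 |
|---|---|---|---|---|---|
| 25% | 34.5 | 34.5/610 = 5.7% | 34.5/469.5 = 7.3% | 1.06-1.07 | 1.11-1.15 |
| 50% | 69 | 69/610 = 11.3% | 69/504 = 13.7% | 1.11-1.14 | 1.23-1.27 |
| 75% | 103.5 | 103.5/610 = 17.0% | 103.5/538.5 = 19.2% | 1.17-1.19 | 1.34-1.38 |
| 100% | 138 | 138/610 = 22.6% | 138/573 = 24.1% | 1.23-1.24 | 1.45-1.48 |

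These are shares of subjects. Exposure-adjusted rates depend on person-time, which the documents do not give. Subjects who move from 150 mg to 300 mg enter both columns, which would lower the share at 300 mg.

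**4. Could the Week 68 primary endpoint analysis (PEA) have answered the objective?** Protocol 3.3 predicts: "Substantially less subjects show a full relapse, the predictions reaching 10% after four months". Week 68 is 16 weeks after randomization, so 276 x 0.10 = 27.6, about 28 placebo relapsers. The first scheduled visit after randomization is Week 56, so none would have more than 68 - 56 = 12 weeks of re-treatment by then. With zero events in n subjects, the one-sided 95% upper limit is 1 - 0.05^(1/n), which is 10.2% for n = 28. Protocol 3.3 calls the prediction highly uncertain, so a range is needed. At 5% relapse n is about 14 and the limit 19.3%. At 25% n = 69 and the limit 4.2%.

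**The case against.** The strongest reply rests on the verb in SAP 1.3. Something that is not re-run was run before. SAP 1.1 says that the plan is mainly for the final analysis and that earlier key analyses may be repeated. The time-to-event table in SAP 1.9.7 separates the PEA cut-off from the end of the withdrawal period, and Protocol 3.5 and 9.6 allow further interim analyses. A re-treated safety analysis after Week 68 may therefore exist, and if it covered the whole period SAP 1.1.1 had nothing to declare. This stands as far as it goes. A reader might infer that the objective was abandoned, or that nearly all re-treated safety data were never tabulated. The documents support neither. Equally, neither document shows an earlier analysis that meets the objective. The PEA is the only one fixed at a study week, and the planned interim at marketing submission is blinded.

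A reader might also infer that restart events are invisible in the final report. They are not: SAP 1.10.1 lists all adverse events, and SAP 1.1 orders listings by treatment sequence, so individuals can be traced. But listings give no incidence or exposure-adjusted rate for a group.

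Nor is pooling itself a departure. Protocol 9.5.2 plans pooled groups for adverse events in addition to the others. What is missing is the separate summary beside them.

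Finally, re-treatment after relapse is not the same as re-exposure after a gap. Secukinumab-arm relapsers had no withdrawal period, while placebo subjects who start secukinumab at Week 156 without relapse are also restarting. This is correct, and the remedy has to separate these groups.

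**Conclusion.** The point holds for the final analysis. A named secondary safety objective gets no separate summary there, its subjects are pooled in every safety table, and the departure from Protocol 9.5.2 is undeclared. How much is lost depends on the data cut of an earlier run that the documents do not describe. If that was Week 68, most re-treatment experience probably came later. If it was Week 156, the gap is mainly the open-label years.

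The dilution figures (a 6% to 24% share, with a doubling shown as 1.06 to 1.24) are illustrations that rest on assumed relapse fractions and an equal dose split. They give Week 156 restarters the same risk as continuous subjects. If restarters share a raised risk, counting every placebo subject as re-exposed gives the 100% row. The figure of 28 relapsers by Week 68 is the protocol's own uncertain prediction applied to planned numbers. No power or alpha result is affected. The SAP should be changed, because the remedy is cheap and lets the final analysis answer the objective.

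**What to change.** - In SAP 1.3, delete the sentence excluding relapsed subjects from the repeated safety analysis.
- Add Placebo - AIN457 150 mg and Placebo - AIN457 300 mg to Table 1-3, as already defined in Table 1-2, counted from the first re-treatment dose. Report adverse events, serious adverse events and adverse events of special interest, as crude and exposure-adjusted incidence.
- Show secukinumab-arm relapsers separately, and placebo subjects who start secukinumab at Week 156 without relapse as their own restart group.
- If an earlier analysis is relied on for part of the period, cite it with its data cut and declare the departure in SAP 1.1.1.
- A separate table for the first 12 weeks after restart is optional.

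Partial responders, named in the same objective, also lack a safety column and could be handled in the same amendment.

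The cost is SAP wording and a few tables from data already collected. Only the Week 156 restart group needs a grouping that Table 1-2 does not supply. The drawback is small cell counts, so the new columns should be read descriptively.

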### 2.3 Exploratory objectives

[figure not shown]
- 
- 
- To explore the effects of treatment with secukinumab with respect to the Health Assessment Questionnaire® – Disability Index (HAQ®-DI) in subjects with psoriatic arthritis (PsA) at baseline of core study over time.

### 3 Investigational plan

#### 3.1 Study design

Figure 3-1 Study design

PFS: prefilled syringe; Week 52 – end of maintenance period in core studies (e.g., CAIN457A2302 or CAIN457A2303) which is randomization (Rand\*) visit for CAIN457A2302E1 (extension study); The screening period will be the duration between signing the informed consent form and randomization registered with Interactive Response Technology (IRT); s.c.: subcutaneous; Week 156 end of treatment period (EoT); Week 260 – open label end of treatment (OL-EoT) period; q4wk – every four weeks; end of follow up (EOF)

★Primary endpoint analysis (PEA) at Week 68; ① PASI 75 Responders: subjects with PASI 75 at Week 52 of core study; ② Partial responders: subjects with PASI 50, but not PASI 75 response at Week 52 of core study; first full relapse – a loss of > 50% of the maximum PASI gain compared to the baseline of core study

(A) PASI 75 Responders entering randomized withdrawal period

Subjects who were PASI 75 **responders** at Week 52 visit of the core studies (e.g., CAIN457A2302 or CAIN457A2303) and have been on secukinumab s.c. 150 mg or 300 mg in the core studies will be randomized to continue same s.c. doses of secukinumab in PFS or receive placebo every 4 weeks up to Week 152. Randomization in each group will be 2:1 (refer protocol text for details)

a. Secukinumab 150 mg PFS group: One s.c. injection of secukinumab 150 mg in PFS plus s.c. injection of placebo secukinumab 150 mg in PFS at randomization (Week 52) and thereafter every 4 weeks up to Week 152 (or until first relapse). Subjects with **first full relapse** will be treated with two s.c. injections of placebo secukinumab 150 mg in PFS once weekly for three weeks (1 week, 2 weeks and 3 weeks later). After 4 weeks following relapse the routine dosing with secukinumab 150 mg regimen every 4 weeks dosing is continued thereafter. Subjects who enter the open label period to continue beyond Week 152 will receive one injection of 150 s.c. every 4 weeks. Starting Week 156, subjects on 150 mg s.c. will have the option to switch to 300 mg s.c. at regularly scheduled visits.

b. Placebo secukinumab 150 mg PFS: Two s.c. injections of placebo secukinumab 150 mg in PFS at randomization (Week 52) and thereafter every 4 weeks up to Week 152 (or until first relapse). Subjects with **first full relapse** will be treated with one s.c. injection of secukinumab 150 mg in PFS plus one s.c. injection of placebo secukinumab 150 mg in PFS once weekly for four weeks (at the visit where the relapse was diagnosed, 1 week, 2 weeks and 3 weeks later). After 4 weeks following relapse the routine dosing with secukinumab 150 mg regimen every 4 weeks dosing is continued thereafter. Subjects on placebo who enter the open label period to continue beyond Week 152 will be treated with one injection of secukinumab 150 mg s.c. in PFS once weekly for four weeks and then one injection s.c. every 4 weeks. Starting Week 156, subjects on 150 mg s.c. will have the option to switch to 300mg s.c. (two injections of 150 s.c.) at regularly scheduled visits.

c. Secukinumab 300 mg PFS group: Two s.c. injections of secukinumab 150 mg in PFS at randomization (Week 52) and thereafter every 4 weeks up to Week 152 (or until first relapse). Subjects with **first full relapse** will be treated with two s.c. injections of placebo secukinumab 150 mg in PFS once weekly for three weeks (1 week, 2 weeks and 3 weeks later). After 4 weeks following relapse the routine dosing with secukinumab 300 mg regimen every 4 weeks dosing is continued thereafter. Subjects who enter the open label period to continue beyond Week 152 will receive two injections of 150 s.c. every 4 weeks.

d. Placebo secukinumab 300 mg PFS : Two s.c. injections of placebo secukinumab 150 mg in PFS at randomization (Week 52) and thereafter every 4 weeks up to Week 152 (or until first relapse). Subjects with **first full relapse** will be treated with two s.c. injection of secukinumab 150 mg in PFS plus once weekly for four weeks (at the visit where the relapse was diagnosed, 1 week, 2 weeks and 3 weeks later). After 4 weeks following relapse the routine dosing with secukinumab 300 mg regimen every 4 weeks dosing is continued thereafter. Subjects on placebo who enter the open label period to continue beyond Week 152 will be treated with two s.c. injections of secukinumab 150 mg in PFS once weekly for four weeks and then two s.c. injections of secukinumab 150 mg s.c. every 4 weeks.

- Refer protocol text for details and for treatment at relapse.

(B) Partial responders not entering the randomized withdrawal period

- Subjects who were **partial responders** at Week 52 visit in core studies (e.g., CAIN457A2302 or CAIN457A2303) and have been on secukinumab s.c. 150 mg or 300 mg in core studies **do not** participate in the randomized withdrawal. These subjects will continue same treatment s.c. dose in PFS (secukinumab s.c. 150 mg or 300 mg) as they were receiving at the time of completing the maintenance period (Week 52) in the core studies. Subjects continuing beyond week 152 will be given open label secukinumab. Starting Week 156, subjects on 150 mg s.c. will have the option to switch to 300 mg s.c. at regularly scheduled visits.

- NOTE: Subjects who are **non-responders** at Week 52 of the core studies (e.g., CAIN457A2302 or CAIN457A2303) are not eligible to enter this extension study, and will complete follow-up visits in the core studies.

Follow-up 2 period: treatment free period only for patients who prematurely discontinued treatment

An outline of the study design is presented in [Figure 3-1](#), while a detailed visit and assessment schedule can be found in [Table 6-1](#). The study design is applicable to other secukinumab phase III studies from which subjects meeting the inclusion/exclusion criteria will potentially enter the extension study CAIN457A2302E1.

This 4 year extension study will include a 2-year double blind period (between Week 52 and Week 156) during which randomized withdrawal analysis will be performed, followed by an additional 2-year open label period (between Week 156 to Week 260). The subjects will receive the last blinded treatment at Week 152. At Week 156, after performing the scheduled study assessments and prior to receiving the first unblinded dose of the study drug, the site will be asked to contact IRT to unblind the study treatment. For subjects who will continue into the open label period, Week 156 will be the beginning of the open label period. The subjects who will not continue into the open label period Week 156 will be the end of blinded withdrawal treatment/treatment period (EoT) at which no study drug will be administered. During the open label period, subjects will receive the last dose of the study drug at Week 256. Week 260 will be the end of open label treatment period (OL-EoT).

Subjects completing the maintenance period (52 weeks) in the core studies (e.g., CAIN457A2302 or CAIN457A2303) will be classified based on Week 52 PASI response as “PASI 75 responders” or “partial responders” or “non-responders”. This Week 52 visit in the core studies is the randomization visit for CAIN457A2302E1 (extension study).

- **PASI 75 Responders**: subjects with a PASI 75 response (subjects achieving  $\geq 75\%$  improvement [reduction] in PASI score compared to baseline of the core study) at Week 52 of core study
- **Partial responders**: subjects with a PASI 50 response (subjects achieving  $\geq 50\%$  improvement [reduction] in PASI score compared to baseline of the core study, but not PASI 75 response) at Week 52 of core study
- **Non-responders**: not achieving at least a PASI 50 response at Week 52 of core study

